#### *10.2 Security arrangements for storage of study data*

1. Paper records containing participant-identifiable information will be stored within the Trial Master File and locked within a secure location in Newcastle Hospitals NHS Foundation Trust.
2. Electronic case report forms containing participant-identifiable information will be held in a password protected server of the Newcastle upon Tyne Hospitals NHS Foundation Trust.
3. Data link-anonymised by trial participant number will be stored in a password-protected server of Newcastle University.

#### *10.3 Access to participant-identifiable data*

Participant-identifiable data will be accessible to:

1. The Chief Investigator
2. Research investigators named in the delegation log for the purposes of carrying out the procedures listed for the study visits in section 6
3. Monitors and auditors from the R&D services at Newcastle upon Tyne Hospitals NHS Foundation Trust upon valid request

Consent for these parties to access trial data will be included within the informed consent process of the study. All individuals who access participant-identifiable data must have a valid contractual relationship with Newcastle upon Tyne Hospitals NHS Foundation Trust. All other researchers that require access to study data (e.g. for the purposes of data analysis) are not permitted to view participant-identifiable information and are restricted to viewing link-anonymised data.

#### *10.4 Collection and storage of ePROMs data*

Remote ePROMs data will be entered by participants directly into the online British Society for Rheumatology (BSR) ePROMs portal. This is a national service provided and maintained by the BSR for use in routine NHS clinical practice, and conforms to all necessary GDPR and Data Protection requirements. The BSR requires that participants complete a separate online consent form within the ePROMs platform before submitting ePROMs data. Submitted ePROMs data will be accessible to the participant's usual clinical team, and to study researchers who have access to the ePROMs portal. Data stored on the BSR ePROMs portal remains available indefinitely, though individual participants can request removal of their data by directly contacting the BSR ePROMs team.

#### *10.5 Collection and storage of digital monitoring device data*

Activity data recorded by Axivity AX6 monitors will be stored within the device, which will be posted back to study researchers by the participant. Data will then be downloaded from the device and stored in a password-protected area of the Newcastle University computer servers. Physiological data recorded by VitalPatch monitors is transmitted wirelessly to the study smartphone, where it is stored until downloaded by a study researcher at the next study visit and then stored in a password-protected area of the Newcastle University computer servers.

#### *10.6 Confidentiality*

Handling of participant-identifiable data will be in accordance with the Caldicott principles and following Newcastle upon Tyne Hospitals NHS Foundation Trust information governance policies.

## **11. FINANCE AND INDEMNITY ARRANGEMENTS**

### **11.1 STUDY FINANCE**

The study is funded by the NIHR Newcastle Biomedical Research Centre. This funding is administered through Newcastle University.

### **11.2 STUDY INDEMNITY ARRANGEMENTS**

The following arrangements will be made for insurance and/or indemnity to meet the potential legal liability of the sponsor(s) or employer(s) for harm to participants arising from the following aspects of the study:

1. Study design - Newcastle University indemnity arrangements will apply
2. Study conduct - NHS indemnity arrangements will apply
3. Study management - NHS indemnity arrangements will apply

## **12. DISSEMINATION OF STUDY RESULTS**

Study results will be presented at scientific conferences and/or published in peer-reviewed journals. All personal identifiable information will be removed from the data during analysis to ensure that the results presented are anonymous. Data will be released from the study after a period of time necessary for the protection of any intellectual property rights.

## **13. QUALITY ASSURANCE**

The conduct of this trial must follow the most current approved version of this protocol, and satisfy the requirements of Good Clinical Practice and relevant policies and guidelines issued by Newcastle upon Tyne Hospitals NHS Foundation Trust and Newcastle University. Monitors and auditors from Newcastle upon Tyne Hospitals NHS Foundation Trust will be able to request access to all study data for necessary quality assurance purposes.

A serious breach[15] of the project protocol or Good Clinical Practice is deemed to have occurred when a breach is likely to effect to a significant degree:

1. "The safety or physical or mental integrity of the subjects of the study"; or
2. "The scientific value of the study"

Suspected serious breaches should be notified to the Sponsor immediately (within 24 hours).

Following consultation with the Chief Investigator the Sponsor should, if it is deemed that a serious breach is suspected, notify the Research Ethics Committee and appropriate regulatory authorities within 7 calendar days of original notification to the Sponsor.

## 15. SCHEDULE OF EVENTS

Activity	Visit 1: day 0	Visit 2: Day 28 (+/- 7 days)	Visit 3: Day 56 (+/- 7 days)	Visit 4: Day 84 (+/- 7 days)	Optional Focus Group (<180 days)
Informed consent	X				
Study eligibility assessment	X				
Medical history	X				
Clinical frailty score	X				
Charlson Comorbidity Index	X				
Height and weight	X				
Concomitant medications	X	X	X	X	
Adverse event recording and reporting		X	X	X	
Joint counts / VAS scores	X	X	X	X	
RADAI-5	X	X	X	X	
HAQ-DI	X	X	X	X	
FACIT-F	X	X	X	X	
MFS	X	X	X	X	
PHQ-2	X	X	X	X	
EQ-5D-5L	X	X	X	X	
Register on ePROMs portal	X				
Instruction on use of remote monitoring devices	X				
Provision of study smartphone and charger	X				
Review of ePROMs record		X	X	X	
Provision of monitoring devices and pre-paid envelope	X	X	X	X	
Collection of study smartphone and charger					X
Bloods (CRP, ESR, FBC, U&Es, LFTs)	X	X	X	X	
Provision of paper questionnaires for next visit	X	X	X		
Experience feedback questionnaire				X	
Optional focus group					X

CRP: C-reactive protein, ESR: erythrocyte sedimentation rate, EQ-5D-5L: EuroQol 5D-5L, FACIT-F: Functional Assessment of Chronic Illness Therapy – Fatigue, FBC: full blood count, HAQ-DI: Health Assessment Questionnaire Disability Index, LFTs: liver function tests, MFS: Mental Fatigue Scale, PHQ-2: Patient Health Questionnaire 2, RADAI-5: Rheumatoid Arthritis Disease Activity Index 5, U&Es: urea and electrolytes.

## APPENDIX A: THE DISEASE ACTIVITY IN 28 JOINTS C-REACTIVE PROTEIN (DAS28-CRP) SCORE

The DAS28-CRP score[1] is calculated using the following parameters:

1. Swollen (SJC28) and tender (TJC28) 28 joint counts\*
2. C-reactive protein (CRP, mg/L)
3. Patient global health assessment (VAS) (visual analogue scale, 0mm = best, 100mm = worst)

$$\text{DAS28 (CRP)} = 0.56\sqrt{\text{TJC28}} + 0.28\sqrt{\text{SJC28}} + 0.36\ln(\text{CRP[mg/l]}+1) + 0.014(\text{VAS[mm]}) + 0.96$$

\* = Where the 28 joints include the bilateral proximal interphalangeal joints, metacarpophalangeal joints, wrists, elbows, shoulders and knees.

Where CRP is below detectable levels, a value of zero will be used for the DAS28-CRP calculation.

The DAS28-CRP score has validated disease activity thresholds [2,3]:

Disease activity	DAS28-CRP threshold
Remission	< 2.4
Low	2.4 ≤ score ≤ 2.9
Moderate	2.9 < score ≤ 4.6
High	> 4.6

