## **8. DATA ANALYSIS**

### *8.1 Correlation between DAS28 and RADAI-5 measurements*

The correlation between paired DAS28 and RADAI-5 measurements taken at each study visit will be assessed by Pearson and Spearman correlation coefficients. DAS28 and RADAI-5 scores will also be dichotomised to binary disease activity values (e.g. high disease activity vs remission/low/moderate disease activity) based on published thresholds, and agreement between categorisation by DAS28 vs RADAI-5 scores assessed by Cohen's kappa statistic.

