### *8.2 Longitudinal RADAI-5 measurements*

Longitudinal changes in RADAI-5 will be visualised by Loess regression. The ability of longitudinal RADAI-5 measurements to discern changes in disease activity will be assessed with reference to the published minimal detectable change in DAS28, and the EULAR response criteria.

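### Setting every undetectable CRP to zero can only push DAS28-CRP down, by up to 0.36 ln(L+1), where L is a laboratory limit the protocol does not state

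*Protocol*

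**What the plan says.** Appendix A gives the DAS28-CRP formula with CRP in mg/L, entering as 0.36 ln(CRP+1), and adds: "Where CRP is below detectable levels, a value of zero will be used for the DAS28-CRP calculation". The same appendix defines low activity as "2.4 ≤ score ≤ 2.9" and moderate activity as "2.9 < score ≤ 4.6", with remission below 2.4 and high activity above 4.6.

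DAS28-CRP is the reference measure in the primary endpoint (Section 2). Section 8.1 uses it in three ways: "The correlation between paired DAS28 and RADAI-5 measurements taken at each study visit will be assessed by Pearson and Spearman correlation coefficients", and both scores are then dichotomised for Cohen's kappa, with the cut illustrated as "e.g. high disease activity vs remission/low/moderate disease activity". In Section 8.2, the ability of RADAI-5 to detect change "will be assessed with reference to the published minimal detectable change in DAS28" and the EULAR response criteria.

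The protocol does not state the CRP assay's detection or reporting limit.

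**The concern.** A result reported as below the limit is a censored value somewhere between 0 and L. The rule replaces all such values by the lowest one possible, so the errors share one sign and do not average out. The logarithm is steepest near zero, so the choice of substitute matters most there. A participant whose CRP moves from just above to just below L loses 0.36 ln(L+1) points with almost no biological change.

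RADAI-5 (Appendix D) contains no laboratory component, so the artefact enters one side of each pair only. Participants are starting a new DMARD, and Section 7.3 expects symptoms to improve in roughly half to three-quarters of them. If CRP falls as well, crossings of the limit would run mostly downward over follow-up. DAS28 improvement would then look somewhat larger than it is, against a RADAI-5 that the rule does not touch.

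**Working it through.** **Inputs.** From Appendix A: coefficient 0.36 on ln(CRP+1); substitute value 0; low band 2.4 to 2.9, width 2.9 − 2.4 = 0.5; high activity above 4.6. Assumed: L, varied because the protocol does not give it. There is no stated figure to reproduce.

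**Direction and maximum.** With zero, the CRP term is 0.36 ln(1) = 0. For a true value c between 0 and L, the score is too low by 0.36 ln(c+1), which is never negative and is bounded by 0.36 ln(L+1). That bound is also the step at the limit.

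**Mean error if c is uniform on 0 to L (assumption).** 0.36 × [(L+1) ln(L+1) − L] / L.

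**Step left if L/2 is substituted.** 0.36 ln(L+1) − 0.36 ln(L/2+1).

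| L (mg/L) | Maximum error and step, zero rule | Mean error, zero rule | Value of the L/2 term | Step left with L/2 |
|---|---|---|---|---|
| 1 | 0.250 | 0.139 | 0.146 | 0.104 |
| 3 | 0.499 | 0.305 | 0.330 | 0.169 |
| 4 | 0.579 | 0.364 | 0.396 | 0.184 |
| 5 | 0.645 | 0.414 | 0.451 | 0.194 |

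**When the step exceeds the low band.** 0.36 ln(L+1) > 0.5 requires L > exp(0.5/0.36) − 1 = 3.01 mg/L.

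**Example near the lower cut-offs (L = 5 assumed).** Tender count 2, swollen count 1, VAS 20 mm. Without CRP: 0.56√2 + 0.28√1 + 0.014 × 20 + 0.96 = 2.31. A CRP just under 5 is set to zero and gives 2.31, remission. A CRP of 5 gives 2.31 + 0.645 = 2.96, moderate. The low category is skipped. With L/2 = 2.5 the censored visit would score 2.31 + 0.451 = 2.76, low.

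**Example at the 4.6 cut (L = 5 assumed).** Tender count 10, swollen count 4, VAS 50 mm. Without CRP: 0.56√10 + 0.28√4 + 0.014 × 50 + 0.96 = 3.99. A true CRP of 4.9 adds 0.36 ln(5.9) = 0.639 and gives 4.63, high. The rule returns 3.99, moderate. The example cut is therefore not immune, but it needs many tender joints together with an undetectable CRP. L/2 would not rescue this case either: 3.99 + 0.451 = 4.44.

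**Correlation.** An illustrative simulation assumed log-normal CRP with median 4 or 8 mg/L; joint counts, VAS and RADAI-5 sharing a latent factor; and a DAS28 SD of about 1.1. The zero rule moved Pearson r from about 0.67 to 0.666 (L = 1), 0.655–0.657 (L = 3) and 0.644–0.648 (L = 5), a fall of roughly 0.02 to 0.03 at worst, with up to 58% of values censored. Classification at 4.6 changed in 0 to 4% of visits. For scale, the Fisher 95% interval for r = 0.66 with 20 participants is tanh(0.793 ± 1.96/√17), about 0.31 to 0.85.

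**The case against.** The rule is explicit, fixed in advance and applied uniformly, and the +1 in the formula makes zero a computable input. It contradicts nothing in the protocol. The study is a pilot of 20 participants that Section 5.4 describes as not statistically powered, and the likely loss in correlation is small beside its sampling error. Half the limit is also a conventional single value. It leaves a step, and it overstates the score when true CRP is below L/2, by up to 0.15, 0.33 and 0.45 for L of 1, 3 and 5. These points stand, and they keep this a modest recommendation.

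Three stronger readings are tempting, and the documents do not support them.

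- **That the step is wider than the low-activity category.** This holds only for L above about 3.0 mg/L. At 1 mg/L the step is half the band. The maximum is also not the typical error: the mean under the uniform assumption stays below 0.5 at every limit from 1 to 5.
- **That the planned kappa is distorted at 2.4 and 2.9.** The only dichotomy named cuts at 4.6, and moves among remission, low and moderate leave it unchanged. It is given only as an example, so a lower cut remains possible, but none is stated.
- **That DAS28 improvement is inflated generally.** The artefact arises when CRP crosses the limit between visits. If CRP is undetectable at both, the substituted term cancels, apart from unknown variation below the limit. The protocol does not say how many participants would cross.

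What the objection does not remove is the one-sided error in the reference measure. It follows from the formula alone and can be reduced at almost no cost.

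**Conclusion.** The point holds as a recommendation, not as a critical flaw. The downward direction is certain. The size is conditional on L: a maximum of 0.25 to 0.65 for limits of 1 to 5 mg/L, and a mean of about 0.14 to 0.41 on the further assumption of a uniform distribution below the limit. With a sensitive assay (L of 1 mg/L or less) the step is at most 0.25 and the comparison with the low band does not apply.

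Within the affected visits, the consequences are greatest for classification among remission, low and moderate activity, and for the change and EULAR-response comparisons of Section 8.2 when CRP crosses the limit. They are less frequent at the 4.6 cut and probably small for the correlations of Section 8.1, a judgement that rests on a simulation with assumed distributions. Without the laboratory limit on record, a reader of the results cannot size the error.

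**What to change.** Replace the sentence in Appendix A with: *Where CRP is reported as below the limit of detection, half that limit will be used; analyses will be repeated with zero and with the limit itself.* Record the laboratory's limit with each CRP result.

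Half the limit cuts the step by more than half at each limit checked (0.25 to 0.10 at L = 1, 0.50 to 0.17 at L = 3, 0.65 to 0.19 at L = 5), and the errors no longer all have the same sign. The two reruns bracket every score that the unknown CRP values could produce.

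The cost is one sentence, one recorded field and two extra analysis runs. CRP is already measured at all four visits, so nothing more is asked of participants. The downside is that some DAS28 scores become slightly higher and a smaller step remains at the limit (0.10 to 0.19 for L of 1 to 5).

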## APPENDIX B : 1987 ACR CLASSIFICATION CRITERIA FOR RHEUMATOID ARTHRITIS

For those participants diagnosed with rheumatoid arthritis before 2010, a retrospective review of the medical records will be performed to ascertain whether they satisfy the 1987 ACR classification criteria as reproduced below. Individual criteria may be cumulatively satisfied at any time point from onset of symptoms.

“For classification purposes, a participant shall be said to have rheumatoid arthritis if he/she has satisfied at least 4 or these 7 criteria. Criteria 1 through 4 must have been present for at least 6 weeks.

### **1. Morning stiffness**

Morning stiffness in and around the joints, lasting at least 1 hour before maximal improvement

### **2. Arthritis of 3 or more joint areas**

At least 3 joint areas simultaneously have had soft tissue swelling or fluid (not bony overgrowth alone) observed by a physician. The 14 possible areas are right or left proximal interphalangeal joints, metacarpophalangeal joints, wrist, elbow, knee, ankle, and metatarsophalangeal joints

### **3. Arthritis of hand joints**

At least 1 area swollen (as defined above) in a wrist, MCP, or PIP joint

### **4. Symmetric arthritis**

Simultaneous involvement of the same joint areas (as defined in 2) on both sides of the body (bilateral involvement of PIPs, MCPs, or MTPs is acceptable without absolute symmetry)

### **5. Rheumatoid nodules**

Subcutaneous nodules, over bony prominences, or extensor surfaces, or in juxta-articular regions, observed by a physician

### **6. Serum rheumatoid factor**

Demonstration of abnormal amounts of serum rheumatoid factor by any method for which the result has been positive in <5% of normal control subjects

### **7. Radiographic changes**

Radiographic changes typical of rheumatoid arthritis on posteroanterior hand and wrist radiographs, which must include erosions or unequivocal bony decalcification localized in or most marked adjacent to the involved joints (osteoarthritis changes alone do not qualify) “

#### APPENDIX C : 2010 ACR/EULAR CLASSIFICATION CRITERIA FOR RHEUMATOID ARTHRITIS

For those participants diagnosed with rheumatoid arthritis before 2010, a retrospective review of the medical records will be performed to ascertain whether they satisfy the 1987 ACR classification criteria as reproduced below. Individual criteria may be cumulatively satisfied at any time point from onset of symptoms.

“Classification criteria for RA (score-based algorithm: add score of categories A–D; a score of 6/10 is needed for classification of a participant as having definite RA)”

	Score
A. Joint involvement	
• 1 large joint	0
• 2-10 large joints	1
• 1-3 small joints (with or without large joints)	2
• 4-10 small joints (with or without large joints)	3
• >10 joints (at least one small)	5
B. Serology	
• Negative RhF & negative CCP	0
• RhF between 19-57 IU/ml OR CCP between 3-9 U/ml	2
• RhF>57 IU/ml OR CCP>9 U/ml	3
C. Acute phase reactants	
• Normal CRP AND normal ESR	0
• Abnormal CRP OR abnormal ESR	1
D. Duration of symptoms	
• <6 weeks	0
• $\geq 6$ weeks	1

“Large joints’ refers to shoulders, elbows, hips, knees, and ankles. ‘Small joints’ refers to the metacarpophalangeal joints, proximal interphalangeal joints, second through fifth metatarsophalangeal joints, thumb interphalangeal joints, and wrists.

#### APPENDIX D : RHEUMATOID ARTHRITIS DISEASE ACTIVITY INDEX 5 (RADAI-5)

The RADAI-5[1] is a self-completed questionnaire consisting of the following five questions, each scored on a 0-10 integer scale:

1. How active was your arthritis in the last six months? (anchors: 0 = completely inactive, 10 = extremely active)
2. How active is your arthritis today with respect to joint tenderness and swelling? (anchors: 0 = completely inactive, 10 = extremely active)
3. How severe is your arthritis pain today? (anchors: 0 = no pain, 10 = unbearable pain)
4. How would you describe your general health today? (anchors: 0 = excellent, 10 = extremely bad)
5. Did you experience joint (hand) stiffness on awaking yesterday morning? If yes, how long was this stiffness? (anchors: 0 = no stiffness, 10 = stiffness the whole day)

The mean value gives an overall “RADAI-5 score”, with validated disease activity thresholds[2]:

Disease activity	RADAI-5 thresholds
Remission	0.0-1.4
Mild	1.6 – 3.0
Moderate	3.2 – 5.4
High	5.6 – 10.0

